## Semler Protocol

**Title of the study:** Measuring Cardiovascular Performance Using Common but Never Compared Methods in Subjects

**Sponsor:** Semler Scientific, Inc.  
[name]  
[name]  
[contact]  
[www.semlerscientific.com](http://www.semlerscientific.com)

[name].  
Chief Executive Officer

This observational study will conduct measurements of cardiovascular performance by echocardiography, Brain Natriuretic Peptide (BNP) blood serum levels and blood flow by volume plethysmography in subjects who meet the AHA/ACC criteria for screening for PAD.

### Research Plan

#### **1. Specific Aims**

The aims of this observational study are to measure these three frequently performed tests: measurements of cardiovascular performance by echocardiography (Echo), Brain Natriuretic Peptide (BNP) blood serum levels and blood flow by volume plethysmography (VP) in human subjects.

#### **2. Background and Significance**

No studies have ever compared these three cardiac performance measures.

#### **3. Description of the Semler QuantaFlo® device**

QuantaFlo® aids clinicians in the diagnosis of vascular disease by measuring blood volume changes in the brachial arterial distributions.

The clinician places a sensor and makes a measurement on an upper extremity. The sensor includes a transducer, which detects changes in arterial blood volume. This signal is digitized and sent to a computer, which runs a specifically-designed software application. The application calculates the result via a proprietary algorithm, which is based on the features of the volume signals from the brachial arterial distributions.

QuantaFlo® is an FDA-cleared device that has been used on more than 1 million patients with no adverse effects reported.

#### **4. Description of Brain Natriuretic Peptide (BNP) Blood Serum Level**

Brain Natriuretic Peptide (BNP) is a hormone secreted primarily by the ventricular myocardium in response to wall stress. BNP levels can be predictive of cardiovascular abnormalities.

The clinician will perform a blood draw to collect some venous blood. The clinician will then send the blood sample to a diagnostic laboratory for evaluation of blood serum BNP levels.

## **5. Description of Trans-Thoracic Echocardiography (Echo)**

Echocardiography is a routine diagnostic test, used to characterize cardiac function.

The clinician places an ultrasound probe at various points on the chest while the subject holds their breath (minimizing lung and chest movement improves image clarity). This allows the Echo equipment to create a model of the heart and compute various cardiac attributes (see Case Report Form).

The Echo equipment used in this study may vary, but all are FDA cleared for computation of LVEF (such as GE Vivid iq, Siemens Syngo US, Phillips Affiniti, Phillips CX50).

## **6. Research Design and Methods**

### **6.1. Objectives:**

- 6.1.1. Collect blood flow data.
- 6.1.2. Measure cardiac performance using echocardiography.
- 6.1.3. Measure blood serum BNP.

### **6.2. Analysis:**

- 6.2.1. Determine the feasibility of conducting these three tests on subjects.

### **6.3. Study Design (note: all study elements must be performed during the same visit):**

- 6.3.1. Investigators will record baseline Demographic information (see Case Report Form).
- 6.3.2. Baseline blood flow 1: Investigators will place the Sensor on the fingertip of the right or left hand and record a **baseline** measurement of blood flow for 15 seconds.
- 6.3.3. Expiration blood flow 1: The subject will then perform forced **expiration** at 30mmHg or more, bearing down for 15 seconds.
- 6.3.4. A disposable mouthpiece will aid in achieving the proper expiration effort.
- 6.3.5. Recovery blood flow 1: After the expiration, the **recovery** blood flow will continue to be measured for 15 seconds.
- 6.3.6. The Subject will rest for at least 1 minute.
- 6.3.7. Baseline, Expiration and Recovery blood flow tests 2 and 3: Another 2 Measurements will be performed, including the Baseline, Expiration and Recovery, for a total of 3 Measurements.
- 6.3.8. Note: The Investigator will verify the outputs from the QuantaFlo Sensor are being recorded, but nothing will be displayed. The Subjects and Investigators will be blinded to the data.
- 6.3.9. A Cardiac Sonographer will obtain echocardiography images for analysis. (**Echo**) (see Case Report Form)
- 6.3.10. Subjects will not learn of the results of the blood flow test or Echocardiogram test.
- 6.3.11. After completion of the blood flow and Echocardiogram tests, the subject will have their blood drawn. Subjects may be informed of the result of the BNP blood test by the physician if desired or if results are abnormal.

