- 6.7.3. Blood will be drawn from the Subject. The Subject will experience pain where the needle enters the Subject's arm and may experience bruising and/or infection at the stick site. Some Subjects may also get lightheaded, nauseous, or faint.

6.8. Data Protection/Privacy:

- 6.8.1. All data will only be handled by the primary investigators listed. Paper copies of the data will be destroyed or locked in the respective investigator's offices. All data will be de-identified at the time of collection. The blood flow and echocardiography data will not be retained in the Subject's medical record. Blood BNP test results may be sent to the subject's medical record if requested by the subject, required by the site, or requested by the principal investigating physician.

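### Section 6.3.10 withholds every echocardiogram result from subjects, with no exception for a clinically important finding, although an abnormal BNP may be disclosed and recorded

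*Protocol*

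**What the plan says.** Protocol 6.3.10 reads: "Subjects will not learn of the results of the blood flow test or Echocardiogram test". Nothing qualifies it. The next item, 6.3.11, sets a different rule for the blood test: "Subjects may be informed of the result of the BNP blood test by the physician if desired or if results are abnormal".

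Section 6.8.1 draws the same line for records. On one side, "The blood flow and echocardiography data will not be retained in the" subject's medical record. On the other, a BNP result may go to the "medical record if requested by the subject, required by the site, or requested by the principal investigating physician". The same section adds: "All data will be de-identified at the time of collection".

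On who sees the echo, 6.3.9 says "A Cardiac Sonographer will obtain echocardiography images for analysis". Section 5 says of the scan: "This allows the Echo equipment to create a model of the heart and compute various cardiac attributes". The Sponsor then reviews the images, which carry only a subject ID, and calculates the measures (6.5.2, 6.5.2.1, 6.5.3). BNP is measured by an outside diagnostic laboratory (6.5.4).

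Neither the protocol text nor the SAP contains a provision for incidental findings, urgent findings or referral.

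**The concern.** The study images the hearts of people in whom disease is expected. Section 7.2.1 anticipates that some will have heart failure, pulmonary hypertension or dyspnea without a known cause. Section 6.4.1.2.1 requires at least 50 people who have risk factors but no symptoms. Clinically important echo findings are therefore foreseeable, and some could arise in people with no symptoms to bring them to a doctor.

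The protocol already accepts that an abnormal research result can justify telling the subject, since it says so for BNP. It makes no such allowance for the test that images the heart directly, and it gives no reason for the difference. What is at stake is subject safety: a serious finding could be seen by someone working on the study and, under the rule as written, not reach the person it concerns.

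**Working it through.** The protocol states no figure on this point to reproduce. The check is a comparison of text, plus a count of the subjects covered.

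**1. The two tests side by side**

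| Question | Echocardiogram | BNP |
|---|---|---|
| May the subject be told? | No, without exception (6.3.10) | Yes, if desired or if abnormal (6.3.11) |
| May it enter the medical record? | No (6.8.1) | Yes, if the subject or principal investigating physician asks, or the site requires it (6.8.1) |
| Who produces the result? | Site sonographer acquires; Sponsor reads and calculates (6.3.9, 6.5.2, 6.5.3) | Third-party laboratory (6.5.4) |

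The BNP record permission depends on a request or a site requirement, not on abnormality. An abnormal BNP can still be both disclosed and recorded. An abnormal echo can be neither.

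**2. Could a finding be noticed?** Yes, at two points. One is acquisition, by a sonographer whose equipment computes cardiac attributes. The other is the Sponsor's planned review. The blinding note in 6.3.8 belongs to the QuantaFlo item. If it were read to cover echo data as well, investigators would also be blinded and the gap would widen.

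**3. Where does the route stop?** Section 6.3.10 does not prevent the sonographer or reader from telling a site physician. It stops the last step, because it says the subject will not learn the result.

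**4. Is withholding needed for valid measurements?** The heading of 6.3 says "all study elements must be performed during the same visit", and 6.3.11 places the blood draw after the blood flow and echo tests. The draw is therefore the last scheduled measurement. Disclosure after it cannot alter any of that subject's measurements.

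**5. How many subjects are covered?**

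- Expected enrolment (6.6.1): 20 per week × 25 weeks = 500.
- Cap (6.4.2.3): 750.
- Minimum asymptomatic group (6.4.1.2.1): 50, which is 50/500 = 10% of expected enrolment, or 50/750 = 6.7% at the cap.

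These percentages give the minimum size of one subgroup, not a rate of missed findings. The documents do not give the rate of important echo findings, the share already diagnosed, or the share that an abnormal BNP would also flag.

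**The case against.** The strongest reply is that 6.3.10 concerns research results. It sits in a list of study procedures just after a blinding note, and the echo measures are calculated by the Sponsor. On that reading a physician could still tell a subject that something needs follow-up, order a clinical echo or write a clinical note, and the defect would be silence rather than prohibition. That reading is possible but not the plain one. The adjacent item uses the word results to include abnormal ones and writes an exception for BNP alone. A work-up outside the study is also not a route that the protocol specifies, and it would leave the subject untold of the result that prompted it.

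The consent forms, verbal consent script and Case Report Form are separate documents that I have not seen, and one of them may contain an incidental-findings clause. That limits what can be said about the whole study package. A clause allowing disclosure would, however, conflict with 6.3.10 as worded, so the protocol would still need amending.

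A laboratory BNP and a research read of images optimised for LVEF could reasonably be handled differently. The documents do not offer that reason, and it would not justify a rule with no exception. It does support keeping the change narrow, since nothing says the Sponsor's read is prompt or clinical.

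Two points stand in full. BNP disclosure is a partial safeguard of unknown overlap, and the number of people affected is unknown.

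**Conclusion.** The concern holds. This is a stated rule with a bad consequence, not a missing detail: followed as written, 6.3.10 keeps an important echo finding from the subject, and 6.8.1 keeps it out of the record. It applies to every subject, about 500 expected and 750 at most, including at least 50 without symptoms. How many would gain new information cannot be estimated from the documents.

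The conclusion rests on the plain reading of 6.3.10 and on the visible protocol and SAP only. I regard it as a required change, because it concerns subject safety, costs little and does not affect the measurements. Section 6.6.2 estimated completion in December 2021 and the SAP is dated 05/17/2022, so enrolment may have ended. The rule has no end date, however, and would still cover findings in images the Sponsor has yet to review.

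**What to change.** 1. Add to 6.3.10: *except that the site physician may inform a subject of an echocardiogram finding that the sonographer or the Sponsor's reader considers clinically important, once that subject's study measurements and blood draw are complete.*
2. Add to 6.5.2 that the reader sends the subject ID of any such finding to the site physician, and that the site keeps the link from ID to subject. Returning a BNP result from an outside laboratory already needs that link, although 6.8.1 describes data as de-identified at collection and mentions no key.
3. Give such findings the same medical-record permission in 6.8.1 that BNP has.

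Item 1 alone removes the prohibition. Because it is a permission, like the BNP rule, item 2 is needed so that the physician hears of what the reader notices. The sponsor and site physicians should define what counts as clinically important and what care follows. Routine echo values and all blood-flow data can stay undisclosed.

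The cost is protocol and consent-form wording, a stated ID link at each site and occasional messages from the reader. Some flagged findings will prove unimportant. No extra scans or reads are required: the exception covers only what is noticed during acquisition or the planned review, and it does not make the study echo a diagnostic service.

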### **6.4. Study Subjects**

#### **6.4.1. Inclusion Criteria:**

- 6.4.1.1. All adult subjects 45 years of age or older will be eligible for enrollment.
- 6.4.1.2. The following groups will also be enrolled:
  - 6.4.1.2.1. At least 50 Subjects from New York Heart Association (NYHA) Class 1 (One or more AHA Risk Factors, asymptomatic),  $\leq 75\%$  (36) Male,  $\geq 25\%$  (12) Female.

6.4.1.2.2. At least 50 Subjects from NYHA Class 2 (symptomatic), ≤75% (36) Male, ≥25% (12) Female

6.4.2. Exclusion Criteria:

- 6.4.2.1. Subjects on mechanical ventilation.
- 6.4.2.2. Subjects who require decisions by a medical power of attorney.
- 6.4.2.3. No more than 750 subjects will be enrolled.
- 6.4.2.4. Subjects unable to safely perform forced expiration.
- 6.4.2.5. Subjects with known technically difficult (TDS) trans-thoracic echocardiographic windows.

6.5. Data Collection:

- 6.5.1. Blood flow data will be collected in the data collection software.
- 6.5.2. Echocardiography images will be reviewed by the Sponsor.
  - 6.5.2.1. All images submitted to the Sponsor shall have personal protected information removed and shall be identified only by the subject ID.
  - 6.5.2.2. Images should be well optimized for assessment of LVEF following current American Society of Echocardiography (ASE) standards for trans-thoracic echocardiography.
- 6.5.3. Echocardiographic measures will be calculated by the Sponsor utilizing methods recommended by the ASE.
- 6.5.4. The blood serum BNP level will be analyzed by a third-party diagnostic laboratory.
- 6.5.5. All results will then be entered into spreadsheets for further analysis. Personal data will be de-identified by giving each subject a unique study code.

6.6. Feasibility and Time Frame:

- 6.6.1. Estimated recruitment of 20 subjects per week (at 3 Sites) is expected with an estimated time frame for completion of approximately 25 weeks.
- 6.6.2. The estimated completion date is December 2021.

6.7. Potential Risks:

- 6.7.1. The blood flow and echocardiography measurements are entirely non-invasive, presenting no known risks to the Subject.
- 6.7.2. The Subject will be asked to perform a forced expiration, which is routinely done in tests of pulmonary function. Forced expiration may cause lightheadedness and abnormal cardiac rhythm.
- 6.7.3. Blood will be drawn from the Subject. The Subject will experience pain where the needle enters the Subject's arm and may experience bruising and/or infection at the stick site. Some Subjects may also get lightheaded, nauseous, or faint.

6.8. Data Protection/Privacy:

- 6.8.1. All data will only be handled by the primary investigators listed. Paper copies of the data will be destroyed or locked in the respective investigator's offices. All data will be de-identified at the time of collection. The blood flow and echocardiography data will not be retained in the Subject's medical record. Blood BNP test results may be sent to the subject's medical record if requested by the subject, required by the site, or requested by the principal investigating physician.

**7. Human Subjects**

**7.1. Detailed Description:**

- 7.1.1. Enrolled subjects will have a brief non-invasive measure of blood flow and cardiac performance using commercially available devices (plethysmography and echocardiography), and performed by experienced, credentialed technicians.
- 7.1.2. Enrolled subjects will have a routine blood draw using commercially available devices and performed by experienced, credentialed technicians.
- 7.1.3. Subjects will be compensated for their participation in this study.

**7.2. Population:**

- 7.2.1. Some subjects may have heart failure, pulmonary hypertension or unexplained dyspnea. The average age will likely be ~60 years of age with an equal distribution of men and women.

**7.3. Recruitment of Subjects:**

- 7.3.1. Subjects will be recruited by the investigative center. Consent for the procedure shall be obtained and the investigative center will discuss the risks and benefits of each procedure. The subject will be asked to sign the attached HIPAA statement for usage of their medical information. Subjects will not be consented if they have received any sedating medications such as fentanyl, morphine, Versed or Ativan.
- 7.3.2. Script for Verbal Consent (See 35-0173 QF+ Script for Verbal Consent, Multi-Lingual)

**8. Case Report Form (See 35-0174 QF+ Case Report Form, Multi-Lingual)**

**9. Subject Informed Consent Form**

- 9.1. See 35-0175 QF+ Informed Consent Form, English
- 9.2. See 35-0176 QF+ Informed Consent Form, Chinese, Traditional
- 9.3. See 35-0177 QF+ Informed Consent Form, Spanish, Mexico
- 9.4. See 35-0178 QF+ Informed Consent Form, Vietnamese
- 9.5. See 35-0179 QF+ Informed Consent Form, Chinese, Simplified

Title: Clinical Trial – Statistical Analysis Plan

Date: 05/17/2022

Study Title:

Measuring Cardiovascular Performance and Blood Flow Using Common But Never Compared Methods

Trial # NCT04553484

Title: Clinical Trial – Statistical Analysis Plan

QuantaFlo® Plus Statistical Analysis Plan

A line listing, a Bland-Altman plot, and error plots (for both individual test subjects and all subjects pooled), and rationale for any points excluded from analysis on 200 or more data points will be generated. Population mean bias (μ_0), between-subject variance ($\sigma_{\mu 2}$), within-subject variance (σ_2), and upper 95% and lower 95% limits of agreement will be included. If the plots show noticeable outliers, the following will be provided:

- test setup, test procedure, and any other factors that may have affected these data points; and
- a discussion of how the outlier(s) do not raise safety and performance concerns regarding the accuracy of the device.

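### The SAP words its outlier discussion so that only a favourable conclusion fits, and does not require the effect of excluded points to be shown

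*SAP*

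**What the plan says.** The whole analysis plan is one paragraph and two bullets under the SAP heading QuantaFlo Plus Statistical Analysis Plan. It asks for a line listing, a Bland-Altman plot and error plots (per subject and pooled), and says that a "rationale for any points excluded from analysis on 200 or more data points will be generated". It then names mean bias and the between-subject and within-subject variances, and states that "upper 95% and lower 95% limits of agreement will be included".

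Outliers come next: "If the plots show noticeable outliers, the following will be provided". The first bullet asks for "test setup, test procedure, and any other factors that may have affected these data points". The second asks for "a discussion of how the outlier(s) do not raise safety and performance concerns regarding the accuracy of the device".

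The Protocol adds no rule on outliers or exclusions. Its only stated analysis (6.2.1) is to "Determine the feasibility of conducting these three tests on subjects", and 6.5.5 says only: "All results will then be entered into spreadsheets for further analysis".

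**The concern.** The first bullet on outliers is neutral: it asks for facts about how the measurement was made. The second is not. It asks the author to explain how the outliers are harmless, when the open question is whether they are. An author who follows it literally has no place to report an outlier that does count against the device. An outlier review is useful only if it can come out either way.

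The secondary point is about what the reader can see. The duty to give reasons for exclusions is a sound disclosure rule. However, the SAP gives no criteria for exclusion and does not require the limits to be shown with the excluded points put back. If large differences happened to be among those points, the reported limits would be too narrow, and no required table would show by how much.

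**Working it through.** **1. Wording.** There is no plan figure to reproduce: the documents give no SD, outlier rate, exclusion cut or acceptance limit. The check on the main point is a reading of the two bullets side by side.

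- Bullet 1 (setup, procedure, other factors) can be completed honestly whatever the cause of the outlier.
- Bullet 2 can be completed as written only if the outlier raises no concern. Nothing in the SAP or Protocol says what to write otherwise.

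**2. Which points the limits use.** The SAP speaks of points excluded from analysis, then lists the statistics to be included. On the ordinary meaning, those statistics use the retained points. No second set is asked for. The SAP also does not say whether "200 or more data points" is counted before or after exclusion.

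**3. Illustration of how exclusions could affect the limits.** Input from the SAP: 200 points, 95% limits. Assumptions: independent normal differences, and points dropped by size at c SDs from the mean.

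- SD ratio after dropping: r = √(1 − 2c·φ(c)/(2Φ(c) − 1))
- True coverage of the nominal 95% limits: 2Φ(1.96r) − 1
- Expected number dropped: 200 × 2(1 − Φ(c))

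Example, c = 2.5: φ = 0.01753 and 2Φ − 1 = 0.98758, so r = √(1 − 5 × 0.01753/0.98758) = 0.955.

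| Cut c (SD) | Points dropped of 200 | r | Narrowing | Coverage |
|---|---|---|---|---|
| 3 | 0.5 | 0.987 | 1.3% | 94.7% |
| 2.5 | 2.5 | 0.955 | 4.5% | 93.9% |
| 1.96 | 10.0 | 0.871 | 12.9% | 91.2% |

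**4. Scale against sampling error at 200 independent points.**

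- SE(SD)/SD = 1/√398 = 5.0%
- SE(limit)/(1.96 SD) = √(1/200 + 1.96²/398)/1.96 = 6.2%

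The two milder cuts fall below both figures. The 1.96 SD cut exceeds them but is an extreme case. Unlike sampling error, dropping by size acts in one direction only.

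**5. Heavier tails (also assumed).** Suppose 1%, 2.5% or 5% of 200 points have 4 times the SD, and that many of the most extreme points are dropped. By simulation (4,000 runs each), the limits shrink to about 92%, 83% or 72% of the all-points width and cover about 94%, 92.5% or 90%.

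**6. How often would the outlier bullets apply to a fault-free device?** The SAP does not define a noticeable outlier, so a cut must be assumed. For 200 independent normal points, P(at least one beyond c) = 1 − (2Φ(c) − 1)^200, which is 42% at 3 SD and 92% at 2.5 SD. Points within a subject may be correlated. With 67 subjects × 3 points and an intraclass correlation of 0.8 (both assumed), simulation gives about 34% and 84%. The answer depends mainly on the cut.

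**The case against.** **The SAP is already fairly transparent.** It requires a listing, individual and pooled plots, reasons for exclusions, and a factual account of outliers. This stands in part. If the excluded points appear in the listing, a reader could recompute the limits, but the SAP does not say that they do.

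**The analysis set is not truly ambiguous.** This stands. A reader might infer that the SAP leaves open which points the limits use, but the phrase about exclusion from analysis points to the retained ones. What is missing is a view of what the exclusions did.

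**The SAP does not license trimming.** This stands. A reader might infer that large differences may be dropped at will, or that an outlier under the bullets is the same thing as an excluded point. The SAP says neither. Exclusions for technical reasons need not narrow the limits at all.

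**Every paired point need not be primary.** This also stands. Such a rule would force in measurements that breach the Protocol's own test conditions, such as the expiration pressure and duration or the rest interval in 6.3, or images not well optimised for LVEF (6.5.2.2). Technical exclusions can be legitimate.

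**The outlier clause may never be triggered.** This cannot be settled. A reader might infer from step 6 of the working that it will probably be needed, but with no definition of noticeable and a probability below one half at 3 SD, the documents do not support that.

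None of these answers the main point: the wording of the second bullet is one-sided whether or not it is triggered.

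**Conclusion.** The main point holds on the text alone and needs no assumption: the second outlier bullet presupposes a favourable conclusion about device accuracy. It affects the discussion only and changes no estimate.

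The secondary point holds in a limited form: no exclusion criteria are given, and no result showing the effect of exclusions is required. The narrowing figures rest on assumed normality, independence and dropping by size, none of which the SAP states. They show only that the effect could range from negligible to noticeable.

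A reader might go further and infer that the device's result is fixed in advance. The documents do not support this, since the SAP sets no pass/fail limit and the numerical results are not constrained by the bullet. The point is minor.

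**What to change.** 1. In the second outlier bullet, change *how* to *whether* and delete *do not*, so that the discussion can reach either conclusion.
2. Add a rule: if any point with both values available is excluded, bias, variance components and 95% limits are reported both with and without the excluded points, and those points are flagged with reasons in the listing and plots.
3. State that exclusions rest on technical criteria set without sight of the difference between device and comparator. The SAP is dated 05/17/2022 and Protocol 6.6.2 estimated completion in December 2021. It should therefore not be taken for granted that the criteria came before the data, and the SAP should say who set them and what they had seen.

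The cost is a few words of SAP text and, only if points are excluded, one extra table. The limits with the excluded points restored may be somewhat wider. No new data are needed.
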